8.1 Study population

Participants are male and female UK-based military veterans who suspect, or know, they have a diagnosis of PTSD and/or CPTSD.

8.2 Eligibility criteria

8.2.1 Inclusion criteria:

- UK based military veterans from the Royal Navy or Royal Marines, British Army, Royal Air Force;
- Aged >18 years;
- Currently living or working in the UK;
- Ability to read and speak English;
- PTSD diagnosis determined by DMS-5 using the Clinician Administered PTSD scale (CAPS-5)
- Experiencing symptoms causing clinically significant distress or impact on social, occupational or other areas of functioning;
- Self-reported history of exposure to one or more traumas;
- Willing and able to provide informed consent;
- Willingness to be randomised to treatment group;
- Willingness for the therapy sessions to be video recorded.
- Access to the Internet.

8.2.2 Exclusion criteria:

- Currently receiving psychological treatment for PTSD;
- Currently has a comorbid DSM-5 mental health or personality disorder sufficiently severe as to intrude upon the participant's ability to cooperate with treatment.
- Participants who have had a self-reported suicide attempt within the past month;
- Current dependence on alcohol as determined by an AUDIT cut off of ≥20 [76] or self-report of prescription or illegal substances dependence.
- An existing dissociative disorder as determine by scoring ≥43 on the Dissociative Experiences Scale [77]
- Self-reported medication changes in anti-psychotic and anti-depression medication in the previous four weeks.
- Any other documented reason in which the assessing assistant psychologists, in consultation with their clinical supervisor, determine that treatment for other mental health symptoms takes precedent over their PTSD at the time of assessment.

8.3 Participant recruitment strategy for all phases of the project

8.3.1 Recruitment campaign

We will use a funded and targeted UK-wide social media campaign which will be supported by existing and establishing new networks though the PPIE group, the veteran charity sector and regimental sectors and veteran research groups. This method and collaboration was successfully used in the feasibility trial.

1) Nativve Health Research (https://www.healthresearch.study) will develop a targeted social media digital advertising campaign. Their algorithms target veterans living in specific UK regions and with specified age, ethnic and gender profiles. The veteran community has a high social media presence and the campaign will use the following platforms: FaceBook, Instagram and X, formally known as Twitter. We expect high levels of organic veteran community traffic "likes" and "shares". The social media campaign will support recruitment

of veterans who have not remained close to their regiments or engaged with local veteran charities. The social media campaign will be developed to ensure it reaches women, older veterans of 70 years and over and ethnic minority veterans. The campaign will be escalated/de-escalated according to study needs each month to support the recruitment targets. The website design will be inclusive. We aim for our randomised population to be a minimum of a) 3% from an ethnic minority, b) 14% women and c) 20% veterans \geq 70yrs. There will be no upper limits on these recruitment targets.

- 2) We will advertise our research to women veterans via the Centre for military women's research CMWR: Get involved, take part, or collaborate! (centreformilitarywomensresearch.com) and the female veterans cluster of the Confederation of Service charities (Female Veterans - Cobseo) and via the Female Veterans UK Facebook Group.
- 3) We will engage with the UK-wide veteran charities that supported recruitment to our feasibility trial and were involved in our dissemination work using traditional and online media announcements, as well as reaching out to new veteran charities and the Regimental Sector to tell them about our study and invite them to support us with recruitment. We will offer online seminars and 1:1 meetings to explain our work and support the establishment and delivery of recruitment pathways as proved successful in the feasibility trial. We will promote awareness of the study using our Institutions' and funders' social media feeds and relevant media outlets. Our PPIE group and experienced members of the research team will identify the charities and Regimental Sectors that we should establish relationships with.

8.3.2 Expressions of interest

Through exposure to study information through the channels above, potentially interested participants will access our study website where they will find further details about the study and a link to the participant information sheet. Some potential participants will be supported to engage with the study website by their family, regimental peers or the charity sector although we expect the majority to self-refer. The website will signpost veterans who decide not to take part to veteran organisations and NHS helplines who offer support. Those veterans interested in finding out more about taking part will register their eligibility and interest by submitting their contact details directly to the King's study email inbox via the study website. All potential participants leaving their contact details will be contacted by a named member of the research team via our study email or telephone.

8.3.3 Eligibility screening

- 1) Initial self-reported screening via the website.
- 2) Following expression of interest, potential participants will be asked to complete the online PCL-5 scale to screen for the severity and breadth of PTSD symptoms [22] and the AUDIT questionnaire [76] to screen for alcohol dependency. If they score >32 on the PCL-5 and <20 on the AUDIT, potential participants will be asked to complete informed consent by a member of the trial management team and they will be invited for an eligibility confirmation assessment via videocall within two weeks.

8.3.4 Eligibility confirmation assessment

Once informed consent (see details below) is obtained participants awaiting final eligibility confirmation will be given an appointment within two weeks to undertake the 90-minute eligibility confirmation assessment by an assistant psychologist specifically trained for the trial.

The assessment incorporates a PTSD eligibility confirmation interview using the CAPS5[23], the (ICD-TQ) [25], which will determine the presence of clinically significant PTSD and its subsequent level of complexity and the Dissociative Experiences Scale (DES) [77] to determine whether they have a dissociative disorder which is an exclusion criteria. In addition, a general mental health screening assessment will be completed to identify presence of any mental health exclusion

criteria and determine historical and comorbid challenges including medical, cognitive ability, perceptual disturbances and presence of substance use that could impact their capacity to engage with a course of therapy (i.e therapy-readiness). Those not eligible will be referred back to any referring organisation by the research team, or, if self-referred, supported by a research team member to engage with alternative help from the NHS and/or charity sectors. Participants assessed as eligible to join the study will be randomised into the trial.

8.4 Informed consent procedures

Expressions of interest from the social media campaign will be received in the research email inbox. The research team will email the potential participants with the participant information sheet and a Qualtrics link containing the PCL-5 and AUDIT screening questionnaires. Potential participants can complete these forms independently or with the support of the researcher. They will provide consent for us to process this data which will be deleted immediately, along with any personal contact details, if they are ineligible or decide they no longer wish to explore taking part in the trial. If they score >32 on the PCL-5 and <20 on the AUDIT, a member of the research team will contact the potential participant by phone or email to discuss the study, answer questions and review the informed consent form. Potential participants will have until the close of phase 1 proof-of concept, or phase 2 trial, recruitment periods to consider whether to take part. Once they decide to proceed, informed consent will be undertaken via Qualtrics, either independently or with the support of a researcher. The signed consent form will be co-signed by the researcher using PDF editing software and returned to the participant via email. The electronic consent form will be stored on a secure, password protected server. No hard copies will be kept.

Those veterans who score <33 on the PCL-5 or >20 on the AUDIT or those that are eligible but decline to take part will be signposted to available support services.

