10.8 Trial outcome measures

10.8.1 Trial primary outcome

The post-traumatic stress disorder checklist for DSM-5 (PCL-5) [54, 57, 89] PTSD symptom severity. It is a 20-item self-report measure that assesses the 20 *DSM-5* symptoms of PTSD taking 5-10 minutes to complete. Symptom severity score (range - 0-80) is obtained by summing the scores for each of the 20 items. A PCL-5 cut-off score of >32 indicates likely PTSD. A 5-10 point change represents reliable change and a ≥10point change represents the minimal clinically significant difference (MCID) with the scale having high internal consistency in measuring DSM–5 PTSD symptoms [90].

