7.0 Ineligible participants

- 7.1 King's trained and contracted assistant psychologists under supervision from a Consultant Clinical Psychologist (investigator [name]) will determine whether each participant meets the inclusion and exclusion criteria.
- 7.2 During the eligibility confirmation assessment the assistant psychologist will complete a risk assessment, including the PHQ-9, and if the participant discloses suicidal ideation, the assistant psychologist will discuss this with their supervisor and/or a senior member of the research team to decide what action to take.
- 7.3 Those assessed as ineligible for the study will be signposted to alternative specialist voluntary or statutory services. We will provide a safety signposting flyer with contact details for emergency numbers, military organisations and charities that provide support, and offer tailored individual signposting, where appropriate.
- 7.4 For those ineligible, but assessed as high risk, the GP will be contacted to, where necessary, mobilise crisis response and potential referral to NHS primary or secondary care.
- 7.5 Where safeguarding and vulnerable adult's concerns are identified this will be escalated, acted on and reported to the relevant statutory body safeguarding team.
- 7.6 For any individual deemed at immediate high risk and who is unable to keep themselves safe, emergency services will be contacted directly.

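### Section 8.4 signposts online screen-outs only above AUDIT 20, while exclusion starts at 20, so AUDIT exactly 20 with PCL-5 of 33 or more is screened out but not named for signposting

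*Protocol*

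**What the plan says.** Four statements in the protocol bear on the AUDIT threshold.

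- **Section 8.2.2 (exclusion):** "Current dependence on alcohol as determined by an AUDIT cut off of" ≥20.
- **Section 8.3.3 (passing the online screen):** "If they score >32 on the PCL-5 and <20 on the AUDIT", the person moves on to consent.
- **Section 8.4, main paragraph:** the same pass rule, PCL-5 >32 and AUDIT <20. It also says that the screening data and contact details of someone found ineligible are deleted at once.
- **Section 8.4, closing sentence (signposting):** "Those veterans who score <33 on the PCL-5 or >20 on the AUDIT", plus those who qualify but decline, are pointed to support.

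Three other places mention support for people who do not enter the trial.

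- **Section 8.3.2:** "The website will signpost veterans who decide not to take part to veteran organisations and NHS helplines who offer support".
- **Section 8.3.4:** people found ineligible at the confirmation assessment are referred back or helped to find other care. That assessment follows consent.
- **Appendix 1, item 7.3:** "Those assessed as ineligible for the study will be signposted to alternative specialist voluntary or statutory services". No score threshold is given.

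**The concern.** The closing sentence of section 8.4 is evidently meant to catch everyone who fails the online screen. Its PCL-5 limb does this: below 33 is the complement of above 32. Its AUDIT limb does not: above 20 is not the complement of below 20. The third limb, for those who qualify but decline, cannot help, because someone at AUDIT 20 does not qualify.

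If the screening logic or staff instructions are built from section 8.4 as written, a person at AUDIT 20 with PCL-5 of 33 or more gets neither an invitation nor a support referral under that rule. By the protocol's own definitions this person meets the alcohol-dependence exclusion and scores in the likely-PTSD range (section 10.8.1). Because contact details are deleted on ineligibility, an omission at this step could not readily be put right later.

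**Working it through.** **Inputs**

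- The PCL-5 score "is obtained by summing the scores for each of the 20 items" and ranges from 0 to 80 (section 10.8.1). Taking whole-number scores, that is 80 − 0 + 1 = 81 possible values.
- AUDIT is taken as a whole number from 0 to 40. The protocol does not give the maximum, so 40 is an assumption. The result does not depend on it.
- Proceed rule (sections 8.3.3 and 8.4): PCL-5 >32 **and** AUDIT <20, that is, PCL-5 ≥33 and AUDIT ≤19.
- Signpost rule (section 8.4, closing sentence): PCL-5 <33 **or** AUDIT >20, that is, PCL-5 ≤32 or AUDIT ≥21.

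**The two rules side by side**

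| AUDIT | PCL-5 0–32 | PCL-5 33–80 |
|---|---|---|
| ≤19 | signposted | proceeds |
| 20 | signposted (PCL-5 limb) | **neither** |
| ≥21 | signposted | signposted |

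**Counts at AUDIT 20**

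- Signposted through the PCL-5 limb: 32 − 0 + 1 = 33 scores.
- In neither set: 80 − 33 + 1 = 48 scores.
- Check: 33 + 48 = 81.

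A full enumeration of PCL-5 0–80 by AUDIT 0–40 agrees. It finds 48 uncovered pairs, all at AUDIT 20 with PCL-5 from 33 to 80, and no pair that falls in both rules.

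**After the correction**

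With AUDIT ≥20 in the signposting sentence, the same enumeration leaves 0 uncovered pairs.

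**Does another section cover the missing cell?**

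- Section 8.3.2 is addressed to veterans who choose not to take part, not to those screened out.
- Section 8.3.4 applies after consent: once consent "is obtained participants awaiting final eligibility confirmation will be given an appointment within two weeks". Someone at AUDIT 20 is stopped before consent and never reaches that appointment.
- Appendix 1, item 7.3, has no score limit, so on a broad reading it applies. But item 7.1 has the assistant psychologists deciding eligibility, and item 7.2 says "During the eligibility confirmation assessment the assistant psychologist will complete a risk assessment". In that setting, item 7.3 reads most naturally as covering people who have had that assessment.

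**The case against.** The strongest reply has three parts.

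**Appendix 1 may already provide the support.** Section 7.0 of that appendix is headed for ineligible people in general, and its introduction speaks of potential as well as actual participants. Item 7.3 carries no threshold, and AUDIT ≥20 is one of the exclusion criteria that item 7.1 refers to. This has weight: in practice staff may well signpost such a person. It does not correct section 8.4, which is the only place that states score limits for signposting after the online screen, and the surrounding items leave the reach of item 7.3 uncertain.

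**The sign may be a PDF-reading artefact.** The age criterion in section 8.2.1 appears as an underlined >18, while the synopsis has ≥18, so an underlined > might have lost its underline in section 8.4. This cannot be ruled out from the extracted text. Against it, the extraction kept the underline in section 8.2.1 and kept ≥ for the AUDIT and dissociation cut-offs in section 8.2.2. A look at the PDF page settles it.

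**Nothing inferential depends on it.** This is correct. Every rule that decides entry is consistent, and a careful reader can see what was meant. The 48 scores are also score values at a single AUDIT point, not people. These points limit the importance of the finding but do not make the sentence right.

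**Conclusion.** The point holds as a minor error. The signposting threshold in section 8.4 disagrees with the exclusion criterion and with the pass rule in the same section, and it leaves out one cell: AUDIT exactly 20 with PCL-5 of 33 to 80. The number of people in that cell is unknown and may be small.

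This rests on whole-number scores on both instruments and on the > sign in section 8.4 being as printed. The practical harm is conditional: it arises only if the screening logic or staff follow that sentence literally and item 7.3 of Appendix 1 is not applied to online screen-outs. No eligibility decision, randomisation, sample size, analysis or trial result changes.

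**What to change.** In the last sentence of section 8.4, replace AUDIT >20 with AUDIT ≥20. Alternatively, drop the numbers and signpost everyone who does not meet both screening conditions, which removes the risk of a second mismatch. Check that the online screening logic and staff instructions use the same limit. If Appendix 1, item 7.3, is intended to include people screened out online before consent, add a clause saying so.

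The cost is one changed symbol and a check of the screening set-up, with no effect on the design or the analysis.

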8.5 Assistant Psychologist training and supervision

An experienced clinical supervisor (investigator [name]) will train and supervise the assistant psychologists completing the semi-structured assessments for the study. Following recruitment, the assistant psychologists will be required to complete self-directed reading on the CAPS-5, DES-11 and ITQ in order to orientate to the assessment tools. Following this they will complete a six-hour training session with the clinical supervisor to train them in the administration of the general mental health screening and CAPS-5 semi structured interview. Following this training the clinical supervisor will observe each assistant psychologist undertake two separate assessments for the supervisor to review for quality assurance purposes. One session will take place during the first four weeks of the trial starting and the second within three months. Following this the AP's will receive regular bi-monthly group supervision with the clinical supervisor to review completed participant assessments that require further review from a senior clinician regarding suitability and ability to engage.

Menta	Mental Health Screening and Assessment Training						
1	Self-directed learning – 2 hours.						
2	Live online teaching face to face by [name] – 6 hours						
3	Successfully undertake – under observation from [name] – eligibility confirmation assessments with two potential trial participants, JK will review to ensure standard of the CAPS-5 is adhered to. (1x 90min session within 4 weeks of completion of the training, then 1x 90min session within 3 months of completion of training) per Assistant Psychologist – 3 hrs						

Table 2: Assistant psychologist training and supervision

Clinical Supervision					
4	Clinical supervision – 1.5 hour group supervision bi-weekly over course of trial				

8.6 Planned interventions and delivery

The experimental therapy, FIRST, uses non-propriety, copyright free, techniques with the intellectual property shared between [name] and King's College London. All participants will be randomly allocated to receive FIRST within three weeks of randomisation or to a waiting list group who will receive FIRST 20 weeks following randomisation.

8.7 Experimental intervention

FIRST is a brief intervention with minimal and non-traumatising exposure to the original stimulus. It is delivered in 3 to 4 x 90-120 minute sessions by a FIRST therapist via videocall. FIRST rewrites the emotional elements of the memory. FIRST therapy will be delivered over a minimum of three days and a maximum of four weeks. The two factors determining this are a) there must be one sleep cycle between each therapy session and b) scheduling of therapy sessions for the participant and the therapist. The evidence to date indicates that therapy should be completed within four weeks. The FIRST protocol incorporates 18 steps in five stages (table 3). Participants will be asked at all data collection timepoints if they have undertaken any additional therapy for other mental health symptoms such as mood or anxiety, as well as any additional therapy for PTSD.

Stage	Clinical technique	Theory/evidence for the technique
Pre- randomisation assessment by DES [77]	The potential participant is assessed to determine their ability to manage their own association and dissociation processes for suitability of the FIRST protocol.	Participants scoring <31 on the DES-11 proceed as per therapy protocol. Go point 1. Participants scoring between 32-42 (referred to as High DES-11 in following text) proceed with therapist treating them as if the client has complex PTSD and an active dissociation mechanism and modifies therapeutic protocol. GO point 1. Participants with DES-11 score ≥43 should have been excluded prior to randomisation. STOP point
i). Priming process	Prior to commencing work with a trauma memory, the client is primed to the process by completing a full run through of the key elements of the protocol on a neutral memory experience.	 Associational learning provides the opportunity during the priming process to strengthen prefrontal cortex synapses required for memory reconsolidation and alteration in decision making processes [66]. NLP trauma therapy techniques use priming processes before the client engages with the trauma story [21, 29, 78]. If the client has a high DES-11 score at assessment, the protocol follows a revised 'neutral activity double dissociation' visual format at this point. If the client can manage this they proceed into the protocol treatment. – GO point 2. If the client cannot follow the revised visual format

Table 3. The FIRST Protocol and therapeutic Stop/Go points

		on a neutral activity at this point, they do not proceed. STOP point 2. (See Appendix 1 – safety protocol for how we See safety protocol for how we manage trial withdrawal for these participants.)
ii). Desensitisation process through dissociation	A series of black and white movie repetitions of the trauma event are observed from a twice or doubly dissociated position	The NLP trauma therapy techniques utilise modified variations of black and white movie formats to facilitate dissociation from trauma memory and response [21, 29, 36]. Fear cascade mechanism and the neurobiology of dissociation enables the management of hyperarousal, flashbacks, any derealisation process including dissociation in response to trauma, splitting or collapse mechanisms before the client is required to access an associated memory structure [79, 80].
iii). Undoing of trauma memory through reversed imagery	A fast associated, re- experiencing the trauma memory in their own body, as a reversed or run backwards imagery of a trauma memory	Individuals with PTSD have a maladaptive response to processing emotions and are stuck in a trauma response that continues to activate a hyperarousal response when certain triggers occur, effectively resulting in the individual continually reliving the trauma experience. By using a fast associated reversed imagery of a trauma memory found in NLP Trauma Therapies [21, 28, 29, 36] associational learning and adaptive responses are altered and afforded the potential for reconsolidation in the final stage of the processes [81, 82].
iv) Reconsolidation	A new story to the memory is developed which rewrites the emotional elements of the original memory	Rewriting the emotional elements of the memory takes advantage of the hypothesised phenomenon of reconsolidation [32, 83-85]. Reconsolidation describes the reactivation of long term, otherwise permanent memories, by their evocation in certain contexts. When a memory is reactivated, it labilises, that is, it becomes subject to change. By changing the circumstances surrounding the memory and if the new circumstance provides evidence that a threat of negative emotional stimulus is no longer relevant, the strength of the affective charge may decrease. One NLP Trauma therapy which shares some characteristics with FIRST, RTM, is theorised to use the mechanism of reconsolidation to enable the rewriting of trauma memories [27, 31].

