8.10.2 Comparison intervention

Participants randomised to the waiting list control (WL) group can continue with any ongoing care or newly engage with usual care pathways available in NHS veterans' services and charities for non-PTSD mental health concerns. Participants will be offered FIRST therapy following the completion of data collection at 20 weeks post randomisation. They will be informed of the appointment date/time for FIRST therapy commencement at the point of randomisation. Safety data is collected at six and 12 weeks and our well-performing feasibility study safety protocol will ensure that any escalation of symptoms in waiting list participants will be detected and recorded as

an adverse event (Appendix 1).

9 Phase 1: Proof of concept study

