9.4 Progression criteria

We will consider POC on the basis of the progression criteria detailed in table 5. These incorporate criteria and procedures to identify early signals that FIRST may/may not be working, two stop/go points are in the protocol (table 4) and observation of the PCL-5 MCID of 10 points (see analysis below). In the feasibility trial, 4 of 35 participants were deemed unsuitable by the therapist for the RTM protocol. Inability to stay in a neutral state and avoid emotional trauma flooding (becoming overwhelmed by their emotions) when sympathetic arousal was observed were the main reasons. Emotional trauma memory flooding is a contraindication for both RTM and FIRST protocols as ability to cognitively dissociate from the trauma experience is essential to the protocol delivery. Eligibility criteria will assess for this using the DES-11 [77] (see eligibility criteria and table 4).

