9.5 Analysis

The statistical analysis plan (SAP) outlining all the analyses of the POC data will be developed during the trial set up period and before completion of the POC and will be signed off before any data analysis commences. In summary, the mean change from baseline to 12 weeks on PCL-5 scores of the FIRST POC cohort will be compared to the RTM arm data collected during the PETT feasibility study. We will estimate the mean and CI of the change in PCL-5 between baseline and 12 weeks, for the two cohorts. We will then compare them using both the mean change from baseline and the CIs of the mean change. We expect the CIs to be of similar width and to largely overlap if the treatment effect signal in the POC is similar to the treatment effect signal in the feasibility. We will compare the total number of therapy minutes of both RTM and FIRST therapy sessions completed to achieve the effect signal.

Table 5. POC study progression criteria using traffic light system (green represents 100%)
concordance with planned targets)

Progression criteria No (%) of (potential) participants		Rationale				
Eligible to proceed to	30 (100%)	In the feasibility trial 4/35 (11%) of participants				

receive FIRST therapy	≥27/30 (11%) <27/30 (>11%)	had contraindications to receiving RTM, identified post-randomisation at therapy commencement. We will evaluate our new general mental health eligibility assessment processes (pre- randomisation) to determine participants are FIRST-therapy ready.
Therapy toleration	≥25 (83%)	PTSD does not resolve itself without treatment so between and 15 and 30 participants (50% or
	15-24 (50- 82%)	over) tolerating therapy offers significant potential treatment gain.
	<15 (50%)	
Efficacy signal – proportion of participants	≥14 (45%)	Our feasibility trial found 48.5% of RTM participants met the 10-point MCID PCL4
reaching the 10-point MCID reduction at 12 weeks	9 -13 (30- 44%)	reduction at 20 weeks. PTSD does not resolve itself without treatment so with the potential of an efficacious brief therapy an equivalent efficacy
WEEKS	<9 (30%)	signal in at least 30 participants (50%) offers significant potential treatment gain.

10 Phase 2: Trial

The randomised controlled trial will run for 19 months with a five-month internal pilot. Data collection will continue up to the 20-week primary outcome timepoint for both arms of the study with 52-week maintenance of effect data collected for the Intervention arm only (see Appendix 2).

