The SAP will also outline the Mediation analysis to test any predefined mediator. [116] Analyses will be conducted using the STATA 17 software. iii) The Mechanisms study primary outcome analysis will estimate the difference in Emotional Stroop task reaction time at 12 weeks between the two treatment groups (FIRST vs. WL). A mixed ANOVA test will be used to measure the effect of emotional stroop task reaction time between T1 & T3. Means and standard deviations will be reported. The Statistical Analysis Plan will outline the analysis of all the other mechanism outcomes.

We do not anticipate that missing data will be more than what has been accounted for in the trial sample size estimation. The level and pattern of the missing data in the baseline variables and outcomes will be investigated. The likely causes of any missingness will be summarised. If data are missing at random, multiple imputation will be used. If, when the missing data are analysed, they present another pattern other than missing at random, we will explore other methods of imputation.

iv) Maintenance of effect will be assessed as an exploratory analysis. Clinical outcome data at 52weeks will be compared to the 20-week trial final endpoint data to determine whether the FIRST group maintained the 20-week PCL-5 scores. The 52-week experimental arm data will also be contrasted with published treatment effect evidence from NICE recommended TF-CBT therapy at the same time point e.g. [58, 59]. This evidence will be compared with FIRST maintenance of effect data to inform NHS dissemination decisions and possibly generate future research questions using FIRST in additional populations living with PTSD to broaden our understanding of the impact of FIRST.

12 Project management

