8.0 Participants that withdraw

- 8.1 Participants that join the study are free to withdraw at any point. In this circumstance responsibility and accountability for the participant's mental health and wellbeing revert or remain with the participant's GP.
- 8.2 Once the research team is aware of the participant's withdrawal they will contact the participant to thank them for taking part in the study and will provide them with the contact details of alternative specialist voluntary or statutory services. They will provide a safety signposting flyer with contact details for emergency numbers, military organisations and charities that provide support, and offer tailored individual signposting, where appropriate.

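### STOP point 2 takes high-DES participants out of the trial after randomisation in the FIRST arm only, so their 20-week PCL-5 is lost on a plain reading and the comparison can lean toward FIRST

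*Protocol*

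**What the plan says.** Table 3 (Protocol section 8.7) splits participants by DES score before therapy. Of the middle band it says "Participants scoring between 32-42 (referred to as High DES-11 in following text) proceed", with an adapted procedure. In the priming stage, a client from that band who cannot follow the adapted format is stopped: "on a neutral activity at this point, they do not proceed. STOP point 2". The same cell points to the "safety protocol for how we manage trial withdrawal for these participants".

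Appendix 1 has no entry for STOP point 2. Its section 8.0 covers people who choose to leave. Responsibility lies with the GP, and the team's only task is that "they will contact the participant to thank them for taking part in the study" and give details of other services. Item 1.3 of the same appendix treats leaving the trial as an alternative end to the 52-week follow-up. Section 10.4 recognises only withdrawal that the participant chooses.

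For the other arm, section 8.10.2 says "Participants will be offered FIRST therapy following the completion of data collection at 20 weeks post randomisation". On missing outcomes, section 11 says "If data are missing at random, multiple imputation will be used", and otherwise other imputation methods will be explored.

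The only rate in the protocol comes from the feasibility trial of RTM, a different therapy. Section 9.4 reports that "4 of 35 participants were deemed unsuitable by the therapist for the RTM protocol", and Table 5 says these people "had contraindications to receiving RTM, identified post-randomisation at therapy commencement".

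**The concern.** A person is randomised to FIRST, begins priming, proves unsuitable for the therapy and is then treated as having left the trial. The reason is a property of the intervention, and it can arise in one arm only before the primary endpoint. If follow-up stops with the therapy, the 20-week comparison sets FIRST participants who could do FIRST against all waiting-list participants, including those who would have failed the same step. That is not the as-randomised effect a superiority trial is meant to estimate.

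No analysis plan can repair this later, because 20-week scores that were never collected cannot be analysed. The follow-up PCL-5 and PHQ-9 are also the trial's safety measures (Appendix 1 item 2.2), so safety data on the same people would go too.

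**Working it through.** **1. The plan's own figures.** Section 10.6 uses a 10-point difference, SD 20, 90% power and a 5% level (two-sided assumed).
- Normal formula: n per arm = 2 × (1.960 + 1.282)² × 20² / 10² = 84.1, so 85. The t-based calculation gives 86 per arm (power 0.903), or 172 in total.
- Allowing 20% loss: 172 / 0.8 = 215.

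Both figures reproduce, so the sample size is not in error. The FIRST arm is 215 / 2 = 107.5.

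**2. Share stopped (f).** The documents do not give it. I take 2% to 11.4% as an assumed range. The upper value is 4/35 = 11.4% from the RTM trial (exact 95% CI 3.2% to 26.7%).

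**3. Formula.** Let Δ be the mean gain in those treated, g the gain in those stopped, and d the number of points by which stopped people would score worse anyway, given baseline.
- Everyone followed: effect = (1 − f)Δ + f·g.
- Stopped people missing from FIRST but their counterparts present in the waiting list: effect = Δ + f·d.
- Difference: f × (Δ − g + d).

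**4. A working therapy: Δ = 10, g = 0, d = 0.** Power is for the as-randomised effect at 86 per arm.

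| f | stopped, of 107.5 | effect, all followed | effect, stopped withdrawn | overstatement | power |
|---|---|---|---|---|---|
| 2% | 2.1 | 9.8 | 10 | 0.2 | 0.895 |
| 5% | 5.4 | 9.5 | 10 | 0.5 | 0.876 |
| 10% | 10.8 | 9.0 | 10 | 1.0 | 0.839 |
| 11.4% | 12.3 | 8.86 | 10 | 1.14 | 0.827 |

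**5. Does the mixed model remove it?** I simulated a random-intercept model with baseline PCL-5 as covariate, weeks 6, 12 and 20, and a time-by-treatment term (108 per arm, total SD 20, intraclass correlation 0.5, 150 runs).
- At 11.4% stopped: −8.84 with everyone followed, −9.97 with stopped participants withdrawn (difference 1.13).
- At 5% stopped: −9.18 and −9.64 (difference 0.47).

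The model does not remove it. A participant with baseline data only is in effect given the course of treated FIRST participants. Imputation under missing at random makes the same assumption.

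**6. A therapy with no effect: Δ = g = 0.** The bias is f·d. SE = 20 × √(2/86) = 3.05, and two-sided type I error = Φ(bias/SE − 1.96) + Φ(−bias/SE − 1.96).

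| f | d | bias | type I error |
|---|---|---|---|
| any | 0 | 0 | 5.0% |
| 5% | 10 | 0.50 | 5.3% |
| 11.4% | 5 | 0.57 | 5.4% |
| 11.4% | 10 | 1.14 | 6.6% |

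**The case against.** **Follow-up is not said to end.** Appendix 1 section 8.0 concerns people who choose to leave and is silent on outcome collection. Items 1.3 and 2.2 distinguish discharge from therapy from leaving the trial, and item 2.2 continues the PCL-5 after discharge. The Table 3 sentence is itself broken. This stands in part: the end of follow-up is the natural reading of withdrawal from the trial, not a stated rule. The protocol does not say that STOP point 2 counts as discharge with continued follow-up, and its wording points the other way.

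**The rate does not fit the rule.** A reader might infer that about 12 of 107 FIRST participants will be lost. The documents do not support that as a forecast. STOP point 2 reaches only DES 32-42, while 4/35 counts all therapist-judged unsuitability for RTM, before the new screening. In Table 5, fewer than 27 of 30 proceeding is red, so 11.4% lies just past the amber limit and the proof-of-concept study could reveal the problem before the trial. This stands, and it is why a range is shown.

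**The direction is assumed.** A reader might infer that the handling certainly favours FIRST. It does so only if Δ − g + d is positive. Baseline PCL-5 and the PTSD/CPTSD stratum may absorb part of any difference in prognosis.

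**Loss allowance.** At 11.4% the stopped participants equal 57% of the FIRST arm's 20% allowance (11.4 / 20). A reader might count that as an added burden. The 20% comes from the same feasibility trial, and the documents do not say whether the four were already inside it.

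**Analysis details belong in the SAP.** The handling of remaining missing data does. Whether questionnaires are still sent after STOP point 2 is a matter for the protocol.

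**Conclusion.** The point holds as a fault in how the protocol handles stopped participants. The stop comes after randomisation, it can occur in one arm only before the primary endpoint, and Table 3 labels it as leaving the trial without provision for continued outcome collection.

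The likely size is modest: about 0.2 to 1.1 points on a 10-point target for 2% to 11.4% stopped, if treated participants gain 10 points, stopped ones gain nothing and follow-up ceases. If FIRST has no effect, there is no bias when baseline-adjusted prognosis is equal. With a prognosis 5 to 10 points worse and 11.4% stopped, type I error is about 5.4% to 6.6%.

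These are conditional figures, since the share stopped and the outcomes of those stopped are unknown. It should still be settled before recruitment, because outcomes not collected cannot be recovered.

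**What to change.** - In Table 3 and Appendix 1 section 8.0, state that STOP point 2 ends FIRST therapy and not participation in the trial.
- Keep collecting the scheduled outcomes from these participants (6, 12, 20 and 52 weeks) unless the participant separately withdraws consent to follow-up.
- In section 11, state that the primary analysis includes all participants as randomised.
- Reconcile Table 3 with section 10.4 and Appendix 1 section 8.0, so that stopping therapy and leaving the trial are separate, defined events.
- Report the number stopped at STOP point 2.

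A sensitivity analysis for the outcomes that remain missing can be left to the SAP. The clinical stop rule does not change. The cost is wording, plus questionnaires and vouchers that are already planned for every FIRST participant.
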